4.2.2.5. Progression-free survival (PFS)

The analysis of BICR-assessed PFS will be performed for R/R MCL patients (phase 1 and phase 2 combined) and phase 2 R/R CLL patients separately and in the same way as DoR. Please refer Table 6 for censoring rules.

4.2.2.6. Time to response (TTR)

BICR-assessed time to initial response and time to best response will be summarized separately using descriptive statistics for R/R MCL patients (phase 1 and phase 2 combined) and phase 2 R/R CLL patients on the tumor response set

4.2.2.7. Investigator-assessed endpoints (DoR, PFS and TTR)

The same analysis methods for BICR-assessed endpoints (DoR, PFS, and TTR) will be applied to investigator-assessed endpoints.

4.2.2.8. Overall survival (OS)

The analysis of OS will be performed in the same way as DoR. Please refer Table 7 for censoring rules.

4.2.2.9. Time to Next Treatment (TTNT, cohort B only)

Time to next treatment (for R/R CLL only) will be performed in the same way as DoR. Please refer Table 8 for censoring rules.

4.2.2.10. Minimum Residual Disease Rate (MRD, cohort B only)

MRD negativity rate will be summarized for phase 2 R/R CLL subjects only.

4.2.3. Safety analyses

4.2.3.1. General considerations for safety

The analysis will be performed separately for all three cohorts: all phase 1 patients, R/R MCL patients (phase 1 and phase 2 combined) and phase 2 R/R CLL patients except where it is mentioned otherwise.

Time windows will be defined for any presentations that summarize values by visit. The following conventions will apply:

- The time windows will be exhaustive so that data recorded at any time point has the potential to be summarized. Inclusion within the time window will be based on the actual date and not the intended date of the visit.
- All unscheduled visit data have the potential to be included in the summaries.
- The window for the visits following baseline will be constructed in such a way that the upper limit of the interval falls half way between the two visits (the lower limit of the first post-baseline visit will be Day 2). If an even number of days exists between two consecutive visits then the upper limit will be taken as the midpoint value minus 1 day. For example, the visit windows for vital signs data (with 1 weeks between scheduled assessments) are:
 - Day 8, visit window 2 – 11
 - Day 15, visit window 12 – 18
 - Day 22, visit window 19 – 25
 - Day 28, visit window 26 – 32
- For summaries showing the maximum or minimum values, the maximum/minimum value recorded on treatment will be used (regardless of where it falls in an interval).
- Listings should display all values contributing to a time point for a patient.
- For visit based summaries
 - If there is more than one value per patient within a time window then the closest value to the scheduled visit date will be summarized, or the earlier, in the event the values are equidistant from the nominal visit date. The listings will highlight the value for the patient that contributed to the summary table, wherever feasible. Note: in summaries of extreme values all post baseline values collected are used including those collected at unscheduled visits regardless of whether or not the value is closest to the scheduled visit date
- For summaries at a patient level, all values will be included, regardless of whether they appear in a corresponding visit based summary, when deriving a patient level statistic such as a maximum.

- Baseline for safety assessments will generally be the last value obtained prior to the first dose of study medication. Alternatively, if two visits are equally eligible to assess patient status at baseline (e.g., screening and baseline assessments both on the same date prior to first dose with no washout or other intervention in the screening period), the average can be taken as a baseline value. For non-numeric laboratory tests (i.e. some of the urinalysis parameters) where taking an average is not possible then the best value would be taken as baseline as this is the most conservative. In the scenario where there are two assessments on day 1, one with time recorded and the other without time recorded, the one with time recorded would be selected as baseline. Where safety data are summarized over time, study day will be calculated in relation to date of first treatment.

Missing safety data will generally not be imputed. However, safety assessment values of the form of “ $< x$ ” (i.e. below the lower limit of quantification) or $> x$ (i.e. above the upper limit of quantification) will be imputed as “ x ” in the calculation of summary statistics but displayed as “ $< x$ ” or “ $> x$ ” in the listings. Additionally, adverse events that have missing causality (after data querying) will be assumed to be related to study drug.

For missing date of initial diagnosis and start dates for AEs, medical history and concomitant medications/procedures, the following will be applied:

- Missing day: Impute the 1st of the month unless month is the same as month of the first dose of study drug then impute first dose date.
- Missing day and month: Impute 1st January unless year is the same as first dose date then impute first dose date.
- Completely missing date: Impute first dose date unless the end date suggests it could have started prior to this in which case impute the 1st January of the same year as the end date.

When imputing a start date, ensure that the new imputed date is sensible e.g., prior to the end date of the AE.

For missing stop dates of AEs, medical history and concomitant medications/procedures, the following will be applied:

- Missing day: Impute the last day of the month unless month is the same as month of last dose of study drug then impute last dose date.
- Missing day and month: Impute 31st December unless year is the same as last dose date then impute last dose date.
- Completely missing: If an AE, MH/medication has a completely missing end date then it will be treated as ongoing. Flags will be retained in the database indicating where any programmatic imputation has been applied, and in such cases, any durations would not be calculated.

For partial subsequent anti-cancer therapy dates, the following will be applied:

- Missing day: If the month is the same as treatment end date then impute to the day after treatment, otherwise first day of the month.

- Missing day and month: If year is the same as treatment end date then impute to the day after treatment, otherwise 1st January of the same year as anti-cancer therapy date.

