3.2.2.1. Adverse events

Adverse Events and SAEs will be collected from time of signature of informed consent form until 30 days after the last dose of study treatment or the start of new anticancer therapy (whichever comes first).

The Medical Dictionary for Regulatory Activities (MedDRA) (MedDRA version 24.0 or later) will be used to code the AEs. AEs will be graded according to the National Cancer Institute Common Terminology Criteria for AEs (NCI CTCAE, latest available version).

Treatment-emergent AEs are defined as those events that occur or worsen on or after the first dose of study drug, through the treatment phase, and until 30 days after the last dose of study treatment or the start of new anticancer therapy (whichever occurs first). AEs occurring before the first administration of IP but increase in severity or frequency on or after administration of IP will be considered as treatment-emergent as well. In the case where it is not possible to define an AE as treatment emergent or not, the AE will be classified by the worst case; i.e. treatment-emergent.

AEs of special interest (AESIs)

The following events are adverse events of special interest (AESIs) for all subjects in this study and must be reported to the sponsor expeditiously irrespective of regulatory seriousness criteria or causality:

Ventricular arrhythmias (e.g., ventricular extrasystoles, ventricular tachycardia, ventricular arrhythmia, ventricular fibrillation, etc.) as defined in Appendix 8.1.1..

Events of Clinical Interest

Some clinical concepts (including some selected individual preferred terms and higher-level terms) have been considered “Events of Clinical Interest” (ECIs) to the acalabrutinib program. ECIs include cardiac events, cytopenias (anemia, leukopenia and thrombocytopenia), hemorrhage, hepatotoxicity, hypertension, infections, intestinal lung disease/pneumonitis, tumor lysis syndrome, and secondary primary malignancies.

These ECIs have been identified as a list of categories provided by the patient safety team. ECIs are defined in Appendix 8.1 and search strategy for narratives are defined in Appendix 8.2.

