4. ANALYSIS METHODS

4.1. General principles

The below mentioned general principles will be followed throughout the study:

- Descriptive statistics will be used for all variables, as appropriate. Continuous variables will be summarized by the number of observations, mean, standard deviation, median, upper and lower quartiles minimum, and maximum. For log-transformed data it is more appropriate to present geometric mean, coefficient of variation (CV), median, minimum and maximum. Categorical variables will be summarized by frequency counts and percentages for each category.
- Unless otherwise stated, percentages will be calculated out of the population total for the corresponding treatment group.
- For continuous data, the mean and median will be rounded to 1 additional decimal place compared to the original data. The standard deviation will be rounded to 2 additional decimal places compared to the original data. Minimum and maximum will be displayed with the same accuracy as the original data. While please refer section 4.2.6 for precision and rounding rules for pharmacokinetic data.
- For categorical data, percentages will be rounded to 1 decimal place.
- SAS® version 9.1 (*as a minimum*) will be used for all analyses.

In general, for all endpoints the last observation before the first dose of study treatment will be considered the baseline measurement unless otherwise specified. For assessments on the day of first dose where time is not captured, a nominal pre-dose indicator, if available, will serve as sufficient evidence that the assessment occurred prior to first dose.

Assessments on the day of the first dose where neither time nor a nominal pre-dose indicator are captured will be considered prior to the first dose if such procedures are required by the protocol to be conducted before the first dose.

In all summaries change from baseline variables will be calculated as the post-treatment value minus the value at baseline. The percentage change from baseline will be calculated as (post-baseline value - baseline value) / baseline value x 100. (If applicable add: For any variable subjected to log transformation, the change from baseline calculated and summarized on the log scale will be back-transformed and presented as a 'baseline scaled ratio' (BSR). Percentage change will then be calculated as (BSR - 1) x 100.)

Data will be presented separately for three cohorts:

- Phase 1 patients
- R/R MCL patients (Phase 1 and Phase 2 combined)

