4.2.5. Concomitant and other treatments

Information on any treatment within the four weeks prior to initiation of study drug and all concomitant treatments, or objective disease progression (whichever is later), with reasons for the treatment, will be recorded in the eCRF. Thereafter, only subsequent regimens of anti-cancer therapy will be recorded in eCRF.

Other anti-cancer therapies, investigational agents, and radiotherapy should not be given while the patient is on study drug.

Medications received prior to, concomitantly, or post-treatment will be coded using the WHODRUG Dictionary Anatomical Therapeutic Chemical (ATC) Classification codes. Concomitant medications will be summarized for the safety analysis set by ATC classification codes.

Prior medications, concomitant and post-randomized treatment medications are defined based on imputed start and stop dates as follows:

- Prior medications are those taken prior to study treatment with a start date or stop date prior to the first dose of study treatment.
- Concomitant medications are those with a stop date on or after the first dose date of study treatment, and for 30 days following the last dose of study treatment (and could have started prior to or during treatment).
- Post-treatment medications are those with a start date after the last dose date of study treatment.

The following summaries will be produced:

- Summary of prior anti-cancer therapies
- Summaries of prior medications and prior radiotherapies
- Summaries of concomitant medications Summary of post study treatment anti-cancer therapies
- Summary of post study treatment radiotherapies

All concomitant and other treatment data will be listed.

Missing coding terms should be listed and summarized as "Not coded".

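### The SAP's single missing start-date rule can place initial diagnosis, medical history and ongoing entry medications on the first dose date

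*SAP*

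**What the plan says.** The scope of the rule in SAP 4.2.3.1 is stated in one line: "For missing date of initial diagnosis and start dates for AEs, medical history and concomitant medications/procedures, the following will be applied". Three cases follow.

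- Day missing: "Impute the 1st of the month unless month is the same as month of the first dose of study drug then impute first dose date".
- Day and month missing: "Missing day and month: Impute 1st January unless year is the same as first dose date then impute first dose date".
- Date fully missing: "Completely missing date: Impute first dose date unless the end date suggests it could have started prior to this". When that exception applies, the imputed value is 1 January of the end-date year.

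The section adds that an imputed start should be sensible, and its only example is that an AE should start before it ends. A medical history item, medication or AE with no end date at all is treated as ongoing.

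SAP 4.2.5 sorts medications using these imputed dates: "Prior medications are those taken prior to study treatment with a start date or stop date prior to the first dose of study treatment". SAP 3.2.2.1 says that when treatment-emergent status cannot be determined, "the AE will be classified by the worst case; i.e. treatment-emergent".

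On baseline, SAP 4.2.3.1 opens by taking, in general, the last value before the first dose. For two Day 1 assessments it adds: "one with time recorded and the other without time recorded, the one with time recorded would be selected as baseline". SAP 4.1 gives the rule for first-dose-day records with neither a time nor a pre-dose indicator: they "will be considered prior to the first dose if such procedures are required by the protocol to be conducted before the first dose".

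**The concern.** For an AE, moving an uncertain start to the first dose date errs towards counting the event as treatment-emergent, which is the safe direction. For something known to precede the study, the same move errs the wrong way. A subject with prior therapy for MCL or CLL was diagnosed before that therapy. A drug in use at entry began before Day 1 whether or not the site could recover the date. At stake is the accuracy of the diagnosis and medical history dates and of the prior-medication summary.

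Two nearby sentences also deserve attention. The exception for fully missing dates does not say what makes an end date suggest an earlier start. The Day 1 tie-break prefers a timed record without repeating that the time must be before dosing.

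**Working it through.** The plan states no figure to reproduce. The check applies the SAP 4.2.3.1 rule literally to test records and then the SAP 4.2.5 definition. The first dose date of 20 November 2020 is an assumption chosen for illustration.

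Rule as applied:

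- Known month is the first-dose month: first dose date. Otherwise: the 1st of that month.
- Only the year known, and it is the first-dose year: first dose date. Otherwise: 1 January.
- Fully missing: first dose date, or 1 January of the end-date year if the exception is invoked.
- Prior medication: imputed start or stop earlier than the first dose.

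| Record | Imputed start | Result |
|---|---|---|
| Diagnosis, fully missing | 20 Nov 2020 | Day 1: impossible after prior therapy |
| Diagnosis, only 2020 known | 20 Nov 2020 | Day 1: impossible after prior therapy |
| Diagnosis, only 2019 known | 1 Jan 2019 | Correct side |
| Medical history, start unknown, ongoing | 20 Nov 2020 | Not before the first dose |
| Medication at entry, start unknown, ongoing | 20 Nov 2020 | Concomitant only |
| Medication, Nov 2020 (true 5 Nov), ongoing | 20 Nov 2020 | Concomitant only |
| Medication, 2020 (true March), ongoing | 20 Nov 2020 | Concomitant only |
| Medication, Oct 2020, ongoing | 1 Oct 2020 | Prior, correct |
| Medication, start unknown, ended 10 Nov 2020 | 1 Jan 2020 | Prior, correct |
| Medication, Nov 2020, ended 10 Nov 2020 | 20 Nov 2020, after its own end | Still prior through its stop date |
| Medication, start unknown, ended 10 Feb 2021, exception invoked | 1 Jan 2021 | After the first dose; concomitant only |
| AE, Nov 2020 | 20 Nov 2020 | Treatment-emergent, as intended |

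The diagnosis rows are impossible because Protocol 5.1 requires at least one prior therapy for MCL (criterion 11) and for CLL (criterion 14).

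Neither guard rescues the affected rows. A diagnosis has no end date. An ongoing item has none either, so the end-date exception cannot act. The sensible-date clause illustrates only start before end, which these rows satisfy.

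The row ending 10 February 2021 shows a separate flaw. When the end date falls in a later year than the first dose, the exception meant for an earlier start returns a date after the first dose.

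For the Day 1 tie-break, the passages can be set side by side. The opening of the bullet and SAP 4.1 both define baseline as pre-dose. Protocol Table 1 (footnote t) requires the indicated Phase 1 Day 1 laboratory samples to be drawn before dosing. But footnote j times the Phase 1 ECG on Cycle 0 Day 1 at 1 to 2 hours after the dose, so a timed Day 1 record can be post-dose by design. SAP 4.2.3.7 summarises ECG change from baseline.

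**The case against.** The strongest reply is that little of this reaches a table. SAP 4.2.4 lists no time since diagnosis. SAP 4.2.4.3 summarises medical history by MedDRA term with no date-based class. SAP 4.2.3.1 keeps imputation flags and does not calculate durations from imputed dates. Affected medications stay in the concomitant summary and in the listings, and prior anti-cancer therapies have their own summary. Records with a known earlier month or year, or with an end before the first dose, are classified correctly. All of this stands. It limits the consequence but does not make the stated rule right for diagnosis or for ongoing entry medications.

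A reader might infer that AEs will leave the treatment-emergent tables by calendar year. With the same assumed first dose, an AE of unknown start ending 20 December 2020 would go to 1 January 2020, and one ending 5 January 2021 to 1 January 2021. That happens only if almost any end date is taken to suggest an earlier start, which would leave the default with almost no work to do for AEs that have an end date. SAP 3.2.2.1 sends undeterminable AEs to treatment-emergent. A date of 1 January 2020 would also ordinarily lie months before AE collection, which begins at consent, while screening tests fall within 28 days of the first dose; it would hardly count as sensible. The documents therefore do not support that inference, though the wording should be tightened.

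A reader might also infer that baseline has no pre-dose check. The same bullet and SAP 4.1 supply one. What remains is that the tie-break sentence does not repeat it.

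**Conclusion.** Wrong as written, but minor. The shared rule can date an initial diagnosis to Day 1 in a previously treated subject. It also removes an ongoing entry medication from the prior summary when its start is fully missing, or known only to the first-dose month or year. The prior-medication summary is the listed output most affected. ORR and the other efficacy endpoints do not use this rule.

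The number of affected records cannot be estimated, because neither document gives a missing-date rate. It would be tempting to assume a rate and cut the prior-medication counts by that share. That does not follow: only ongoing drugs with those particular gaps are affected, and a subject's count changes only if no other record qualifies.

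The conclusion rests on a literal application of SAP 4.2.3.1 and on the SAP 4.2.5 statement that classes use imputed dates. The calendar dates are illustrative; the pattern does not depend on them.

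**What to change.** Limit the first-dose default in SAP 4.2.3.1 to AEs, and treat the other items as follows.

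- Initial diagnosis: impute the earliest date that fits the known parts and falls before the first prior therapy.
- Medical history and medications or procedures: impute a pre-dose date when the item is recorded as present at or before entry; otherwise keep the current rule. The condition matters. Moving every partial medication date to the 1st of the month would turn a drug started on 25 November 2020, recorded only as November 2020, into 1 November and so wrongly into prior.

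Two wording corrections go with this.

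- AEs with a fully missing start: make the exception apply only when the end date is before the first dose date, which agrees with the worst-case rule in SAP 3.2.2.1.
- Day 1 tie-break: take the timed record provided its time is before the first dose; otherwise apply SAP 4.1.

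The cost is a few sentences in the SAP and matching derivation code, plus a check that the eCRF identifies items present at entry. No change to the design or sample size is needed.

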7. DISCONTINUATION OF TREATMENT AND SUBJECT WITHDRAWAL

7.1 Discontinuation of study treatment

Subjects may be discontinued from investigational product in the following situations. Note that discontinuation from study treatment is NOT the same thing as a complete withdrawal from the study.

- Any subject who has objective evidence of disease progression while receiving protocol required study drug should be withdrawn from the study treatment. If there is uncertainty regarding whether there is disease progression, the subject may continue study treatment and remain under disease evaluation until confirmation of disease progression. In particular, transient worsening of disease during temporary interruption of study therapy (e.g., for drug-related toxicity, surgery, or intercurrent illness) may not indicate disease progression. In such circumstances, and if medically appropriate, subjects may resume therapy and relevant clinical, laboratory, and/or radiographic assessments should be done to document whether Tumor control can be maintained or whether actual disease progression has occurred.
- Any adverse event presents a substantial clinical risk to the subject with continued acalabrutinib dosing.
- Subject decision. The subject is at any time free to discontinue treatment, without prejudice to further treatment.
- Pregnancy in a subject, intend to become pregnant or begin breast feeding.
- Severe non-compliance with the Clinical Study Protocol.
- Start of alternative anticancer therapy.
- Study terminated by Sponsor.

See the SoA (Section 1.1) for data to be collected at the time of treatment discontinuation and follow-up and for any further evaluations that need to be completed.

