3.3.1.4. Progression-free survival (PFS) as assessed by BIRC

PFS is defined as the interval from the start of acalabrutinib therapy to the earlier of the first documentation of objective disease progression by the BICR or death from any cause.

Subjects who withdraw from the study or are considered lost to follow-up without prior documentation of disease progression will be censored on the date of the last adequate disease assessment. Subjects who start new anticancer therapy before documentation of disease progression will be censored on the date of the last adequate disease assessment that is on or before the start date of the new anticancer therapy. For patients without an adequate post-baseline disease assessment or no baseline assessments, PFS will be censored on the date of randomization unless they die within 2 visits of baseline.

Table 6 Censoring rules for PFS

Assessment	Outcome	Date of progression or censoring
Death before first disease assessment	Event	Date of death
Documented PD between scheduled visits on or before receiving subsequent anticancer therapy or data cutoff, whichever occurred first	Event	Earliest date of disease assessment documenting progression
Death without documented PD and not receiving subsequent anticancer therapy on or before data cutoff	Event	Date of death
No baseline tumor assessments and it's not known to have died in 2 consecutive visits of baseline	Censored	Date of first dose
No adequate post-baseline assessment and it's not known to have died in 2 consecutive visits of baseline	Censored	Date of first dose
Documented PD or death after subsequent anticancer therapy and the subsequent anticancer started before data cutoff date	Censored	Date of last adequate disease assessment prior to subsequent anticancer treatment
No documented PD or death at the time of data cutoff and subsequent anticancer therapy started before the data cutoff	Censored	Date of last adequate disease assessment prior to subsequent anticancer treatment
Documented PD or death after subsequent anticancer therapy and the subsequent anticancer started after data cutoff date	Censored	Date of last adequate disease assessment on or before data cutoff
No documented PD or death at the time of data cutoff and subject not received subsequent anticancer therapy or subsequent anticancer therapy started after the data cutoff	Censored	Date of last adequate disease assessment on or before data cutoff

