- R/R CLL patients (Phase 2 only)

Demographic data, exposure and safety data will be analyzed based on safety analysis set. Pharmacokinetics will be analyzed based on PK analysis set. Efficacy analyses will be analyzed on tumor response analysis set.

The method for handling missing data is described in the definition for each of the endpoints. Every effort will be made to obtain complete dates for deaths. In the event of a partial or missing death date, the algorithm in Appendix 8.4 will be used.

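### Partial new-therapy dates are imputed without regard to a progression documented after the last dose, so a true PFS or DoR event can become an earlier censoring

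*SAP*

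**What the plan says.** SAP 4.2.3.1 (General considerations for safety) gives two rules for partial dates of subsequent anticancer therapy. Day missing: "If the month is the same as treatment end date then impute to the day after treatment, otherwise first day of the month". Day and month missing: "If year is the same as treatment end date then impute to the day after treatment, otherwise 1st January of the same year". Neither rule refers to a PD date.

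The date matters for efficacy because of the censoring tables. In Table 6 (PFS, SAP 3.3.1.4) this situation is an event: "Documented PD between scheduled visits on or before receiving subsequent anticancer therapy or data cutoff, whichever occurred first". This one is censored: "Documented PD or death after subsequent anticancer therapy and the subsequent anticancer started before data cutoff date", and the censoring date is "Date of last adequate disease assessment prior to subsequent anticancer treatment". Table 5 (DoR, SAP 3.3.1.3) has the same rows.

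For missing data in general, SAP 4.1 states: "The method for handling missing data is described in the definition for each of the endpoints". The endpoint definitions in SAP 3.3.1 contain nothing on partial new-therapy dates, so the rule in 4.2.3.1 is the only one available.

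**The concern.** Both rules place the therapy at the earliest day in the known month or year that still follows the end of acalabrutinib. Protocol 8.1.1.1 and 8.1.1.2 expect the order PD first, then new therapy: where clinically appropriate, new therapy is to be withheld until progression is confirmed. When PD is found after the last dose, the earliest possible therapy date can fall before it and reverse that order on paper. The progression then leaves the analysis and the subject is censored at an earlier scan.

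This removes events from PFS and DoR in subjects who did progress, which lengthens both estimates in a study with no comparator arm. No safeguard is stated. SAP 4.2.3.1 asks that imputed start dates be sensible for adverse events, history and concomitant medications, but attaches no such check to new therapy. No sensitivity analysis on these dates is planned.

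**Working it through.** The plan gives no figure on this point, so there is none to reproduce. The check applies the date rule itself.

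**Notation.** L = last dose (taken as the treatment end date), P = PD date, T = imputed therapy start.

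- Day missing: T = L + 1 if the therapy month is the month of L; otherwise the 1st of the therapy month.
- Day and month missing: T = L + 1 if the therapy year is the year of L; otherwise 1 January.
- Outcome (Tables 5 and 6): event if P ≤ T (a tie is an event); censored if P > T.

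**Who cannot be affected.** Therapy recorded in the month or year of L, or later, always gives T ≥ L + 1. So P ≤ L implies P < T, an event. A flip needs P > T ≥ L + 1, so PD must be at least two days after the last dose. As a check, 200,000 random sequences with P on or before L were run under both kinds of missing date: 0 of 400,000 imputations re-ordered the PD.

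**Who can be affected.** These are subjects who stop for another reason and are followed to PD (Protocol 7.1.2), PD found at an end-of-treatment visit, which may fall up to 7 days after the last dose (Protocol 7.1.1), and a BICR PD dated later than the investigator's.

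**Worked sequences (2022 unless stated).** With the full therapy date, every row is an event.

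| | Last dose | PD | True therapy start | Missing | Imputed | Result |
|---|---|---|---|---|---|---|
| a | 9 Mar | 12 Mar | 25 Mar | day | 10 Mar | censored |
| b | 20 Jan | 10 Mar | 25 Mar | day | 1 Mar | censored |
| c | 20 Jan | 10 Mar | 25 Mar | day, month | 21 Jan | censored |
| d | 15 Nov 2021 | 10 Sep | 1 Oct | day, month | 1 Jan | censored |
| e | 12 Mar | 10 Mar | 25 Mar | day | 13 Mar | event |
| f | 9 Mar | 10 Mar | 25 Mar | day | 10 Mar | event (tie) |
| g | 20 Jan | 10 Mar | 5 Apr | day | 1 Apr | event |

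In row d the imputed start is nine months before the true one.

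**How often an exposed event flips.** The documents give no timing, so the settings below are assumptions: PD uniform on 1 to G days after the last dose, therapy uniform on 0 to H days after PD, 100,000 sequences per setting. Cells show the share of true events censored, day missing / day and month missing.

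| | H = 14 | H = 30 | H = 60 |
|---|---|---|---|
| G = 7 | 0.63 / 0.84 | 0.41 / 0.82 | 0.21 / 0.78 |
| G = 30 | 0.71 / 0.95 | 0.46 / 0.92 | 0.23 / 0.88 |
| G = 90 | 0.73 / 0.97 | 0.47 / 0.95 | 0.24 / 0.90 |
| G = 180 | 0.73 / 0.97 | 0.47 / 0.95 | 0.24 / 0.91 |

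The range is 21–73% with the day missing and 78–97% with day and month missing. These shares apply only to subjects who already have PD after the last dose, therapy on or after PD, and a partial date.

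**Effect of the proposed change.** Rows a and b move to 12 Mar and 10 Mar, ties and therefore events. Rows c and d stay censored in the main analysis. They become events in the sensitivity analysis at 31 December 2022, if that is on or before the cut-off. Rows e to g do not change.

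**The case against.** **The usual path is safe.** Protocol 7.1 says: "Any subject who has objective evidence of disease progression while receiving protocol required study drug should be withdrawn from the study treatment". PD therefore normally falls on or before the last dose. This stands. A reader might infer that any PD in the same month or year as a partially dated therapy is re-ordered. The rule does not do that, because it is anchored to treatment end.

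**The rule is a safety convention.** It sits under a safety heading, and SAP 4.1 sends missing-data handling to the endpoint definitions. Those definitions are silent, so either this rule feeds Tables 5 and 6 or there is none. The placement does not remove the problem.

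**Partial dates should be uncommon.** New therapy is asked about roughly every 12 weeks in follow-up, and a year-only date is the least likely kind. This is reasonable and is why the count is probably small.

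**The true order is unknown, and the earliest date protects the primary endpoint.** This is the strongest point. Suppose drug stops in January without PD, new therapy starts in February, a response is seen in April and PD in October, and only the year of therapy is recorded. A rule driven by the PD date, applied everywhere, would credit the April response to acalabrutinib, which SAP 3.3.1.2 excludes, and would lengthen TTNT. The existing rule avoids both. Any change should therefore be confined to PFS and DoR.

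**Conclusion.** The concern holds for PD documented after the last dose and later than the imputed therapy date. There the SAP censors the PD at an earlier scan even if therapy followed it. The bias favours the drug on PFS and DoR, which are secondary and descriptive. For TTNT the same rule moves events earlier, which is unfavourable to the drug. The primary ORR is touched only if a first response falls after the imputed date.

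The number of subjects cannot be computed, because the documents give no count of partial dates. A reader might infer that each lost event costs 1/33 = 3.0 points in Cohort A or 1/60 = 1.7 points in Cohort B. That is not supported. Turning a Kaplan-Meier event into a censoring drops a factor of 1 − 1/n, where n is the number still at risk at that time. Phase 1 MCL subjects are also pooled with Cohort A, and DoR includes responders only.

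The conclusion assumes that the rule in 4.2.3.1 is applied to the efficacy tables, since no other exists, and that treatment end means last dose.

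**What to change.** State in SAP 3.3.1.3 and 3.3.1.4, for PFS and DoR censoring only:

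- **Day missing:** if a PD by the same assessor as the endpoint (BICR or investigator) falls within the known month, impute the therapy start as the later of the existing imputed date and the PD date. A tie is already an event, so no extra day is needed. Adding one could push the date out of the recorded month.
- **Day and month missing:** keep the existing rule and add a PFS and DoR sensitivity analysis that imputes the latest possible date within the known year.
- **BOR, ORR and TTNT:** keep the existing earliest-date rule, so that responses to later therapy are not credited.

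Cost: a short SAP insertion, a second derived date, a small amount of programming and one sensitivity analysis. The remaining weakness is that PD-first order within the month is assumed, not known, and the SAP should say so.
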